### **Scientific rationale for study designer**

This study is extremely feasible given 1/3 of all 8,000 deliveries performed at Mount Sinai are cesarean sections.

This is a prospective, randomized controlled trial evaluating whether using a barbed suture to close a C-section incision can reduce blood loss. Patients undergoing C-section will be randomized with equal allocation to a barbed suture or a standard antimicrobial suture. The primary outcome is quantification of blood loss (QBL). Differences between the groups will be assessed using a 0.05 level Wilcoxon rank-sum test. Secondary outcomes include time for hysterotomy closure, need for additional hemostatic sutures, rate of endometritis, use of hemostatic agents, and differences in pain which will be assessed by a telephone screening 2 weeks following delivery. The patients will be contacted by study personnel 2 weeks after delivery (they will be instructed on this upon discharge) to discuss pain control, bowel or bladder complaints, and amount of narcotic use necessitated post-operatively. Demographic information will be obtained from the electronic medical record.

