**General Design:** This is a prospective, randomized controlled trial evaluating whether using a barbed suture to close a C-section incision can reduce blood loss. Patients undergoing C-section will be randomized with equal allocation to a barbed suture or a standard antimicrobial suture. The primary outcome is quantification of blood loss (QBL). At Mount Sinai Hospital, QBL is calculated by Triton AI which captures sponge and canister images to accurately monitor blood loss in real time. Differences between the groups will be assessed using a 0.05 level Wilcoxon rank-sum test. Secondary outcomes include time for hysterotomy closure, need for additional hemostatic sutures, rate of endometritis/SSI (superficial wound infection, deep wound infection, and endometritis) within 6 weeks postpartum, use of hemostatic agents, and differences in pain which will be assessed by a telephone screening in the days following delivery. The Mann-Whitney test will be used to compare continuous outcomes between the barbed suture and antimicrobial suture groups. Continuous secondary outcomes include time for hysterotomy closure (in minutes), and difference in pain between post-surgery day 1 and day 14. The Chi-square test or Fisher's exact test (as appropriate) will be used to compare the incidence rate of binary outcomes between the two patient groups. Binary secondary outcomes include need for additional hemostatic sutures (Y/N), endometritis or surgical site infection (SSI) within 6 weeks of surgery (Y/N), and use of hemostatic agents (Y/N). **Inclusion criteria** (1) those undergoing an elective scheduled cesarean delivery at  $\geq 37$  weeks' gestation, (2) those in labor requiring cesarean delivery for usual obstetrical indications, or (3) those who failed a trial of labor after a previous cesarean delivery at Mount Sinai Hospital ages 18-64. **Exclusion criteria include**, multifetal gestations, placenta previas, and patients with a known coagulopathy (DIC, Von Willebrands Disease, etc). Also excluded are patients with IAI, patients on magnesium sulfate, placenta abruption, and PAS.

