### **Recruitment process**

Participants will be identified by their obstetrical provider and research staff as meeting inclusion criteria. The research will be introduced to the patient by their treating physician. Only upon expressed interest will the subject be approached for consent by the study team. The research personnel will be notified by the patient's treating physician of the subject's interest and the research personnel will then obtain official written consent.

Alternatively, to minimize in-person interaction during the COVID pandemic, research staff will identify the patients who are eligible for the study by reviewing the sonography schedule for patients having a nuchal translucency appointment at the correct gestational age, and then reviewing pregnancy history to identify patients who also have had a previous cesarean delivery. A HIPAA Waiver of Authorization has been attached to this submission. We will send a MyChart message/email to those patients (attached) regarding the research study, with patients being able to opt-out of the study at this time. We will then send a copy of the consent form via email (secured RedCap link). They will have the opportunity to review the consent form before we call. Next, we will contact them via phone or Mount Sinai Zoom account to review the consent form and answer any questions from them. This will be documented in EPIC. They can then sign it electronically if they agree to participate. Their participation in the study will be documented in their chart via FYI and their consent form will be scanned and uploaded into media within EPIC.

The research will be introduced to the participants by the patient's obstetrical provider. The obstetrical provider and research team will assess the patient's eligibility for the study and discuss if applicable. A consent form which details the goals and objectives of the study as well as the suture materials will be provided by the provider. Patients will be given the material to read on their own and if interested in participating, a research personnel will obtain formal

written consent and answer any questions. The provider will assess if the patient meets inclusion and exclusion criteria for participation.

Participants will undergo a medical and surgical screening prior to enrollment by their obstetrical provider. There will be no cold contacts with patients.

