#### **Product storage and preparation**

The device will be stored in the locked office of one of the research personnel and will only be handles by the research team until randomization is performed and the patient is allocated to the treatment arm. Only at that time would the research personnel go into the locked office and obtain the suture material for the subject. The material would be then handed off with sterility to the scrub tech who would provide the suture to the surgeon during the procedure

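### The plan does not keep the patient or the pain caller unaware of the arm, so the pain comparison is unprotected against expectation bias; a cheap separation of roles would close the gap.

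*Combined protocol and SAP*

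**What the plan says.** Four places in the combined protocol and SAP bear on this point.

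- **Handling of the allocation (Product storage and preparation).** The suture stays locked away until the patient is randomized. The text continues: "Only at that time would the research personnel go into the locked office and obtain the suture material for the subject". At least one member of the research team therefore knows each patient's arm.
- **Collection of pain (Scientific rationale).** The secondary outcomes include "differences in pain which will be assessed by a telephone screening 2 weeks following delivery". On who calls, it says: "The patients will be contacted by study personnel 2 weeks after delivery". The call also covers bowel or bladder symptoms and narcotic use.
- **Analysis of pain (General Design).** The tested outcome is the "difference in pain between post-surgery day 1 and day 14", compared between arms with the Mann-Whitney test. No pain scale or call script is given, and nothing says who collects the day 1 score.
- **What the patient is told (Recruitment process).** "A consent form which details the goals and objectives of the study as well as the suture materials will be provided by the provider". Whether she later learns which suture was used is not stated.

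Neither of the two design descriptions (General Design and Scientific rationale) mentions masking of anyone. The data-handling section describes coded entry in REDCap and restricted access to the key linking codes to record numbers. It does not restrict who can see the allocation.

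**The concern.** Pain asked about by telephone depends on how the question is put, how the answer is recorded, and what the patient believes about her treatment. If the caller or the patient knows the arm, a modest expectation effect can look like a treatment effect. It cannot be separated out once the data are in.

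The outcome matters to the study's message, because less pain is among the improvements hoped for in the Benefits section. The surgeon must see the suture, but the patient and the caller need not know which one was used. For these two people the exposure can be avoided, and the protocol as written does not avoid it.

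**Working it through.** **1. The plan's own figure.** The only design calculation concerns blood loss. Inputs from the Sample Size section: difference 160.2, SD 371, two-sided alpha 0.05, power 0.85, 15% inflation for the rank test. The two-sample t-test needs 97.3 per group, rounded up to 98. Then 98 × 1.15 = 112.7, rounded up to 113 per group and 226 in total. The stated figure reproduces, and masking the patient and the caller would not change it.

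**2. The roles side by side.**

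| Step | Who | Knows the arm? |
|---|---|---|
| Fetching the suture after randomization | Research personnel | Yes, the person fetching |
| Day 1 pain score | Not stated | Not stated |
| Two-week call | Study personnel | Not stated |
| Patient | Told about the suture materials at consent | Not stated |

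No rule prevents the person who fetched the suture from making the call. No rule keeps the arm from the patient or from another caller.

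**3. What reaches the analysed outcome.** Let b1 and b14 be the between-arm reporting bias on day 1 and day 14. The analysed outcome is a difference between the two days, so it carries b14 − b1. If b1 = b14, the bias cancels. If day 1 is free of bias, all of b14 remains. The documents do not show which case applies.

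**4. Illustrative size.** The documents give no pain scale, SD or bias, so the net bias b is expressed in SDs of the analysed difference and is an assumption. With no true effect and n per arm, using a normal approximation:

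false-positive rate = Φ(b√(n/2) − 1.96) + Φ(−b√(n/2) − 1.96)

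At n = 113, √(113/2) = 7.517. With the plan's 15% rank-test allowance, n = 113/1.15 = 98.3 and √(98.3/2) = 7.01.

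| Net bias b | n = 113 | n = 98.3 |
|---|---|---|
| 0 | 5.0% | 5.0% |
| 0.1 SD | 11.7% | 10.8% |
| 0.2 SD | 32.4% | 28.9% |

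For b = 0.1 and n = 113: Φ(0.752 − 1.96) + Φ(−0.752 − 1.96) = 0.117. All 226 patients are assumed to give both scores. With fewer responders, the same bias gives a somewhat lower rate.

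**The case against.** The strongest reply is that much of this rests on silence, and several stronger readings go beyond the text.

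- **That pain is collected open-label.** A reader might infer this, but no passage says so or says that patients are told their arm. The title and consent pages are not in the supplied text and could carry a masking statement. What the text supports is that masking is not described.
- **That the caller is the person who fetched the suture, or that the whole team knows the arm.** The overlap is at team level only. One section refers to research personnel and the other to study personnel. Neither shows that they are the same individual.
- **That patients are primed to expect less pain.** The Benefits section lists less pain as a benefit to society, after stating that there is no direct benefit. Being told that two materials exist is not being told which one was used.
- **That the error rate is in fact 12% or 32%.** No document supports a particular bias, and the change score may remove part or all of it.
- **That the surgeon-decided outcomes have the same defect.** The surgeon is handed the suture: "The material would be then handed off with sterility to the scrub tech who would provide the suture to the surgeon during the procedure". Knowledge of the arm is unavoidable for additional sutures and hemostatic agents, and labelling them open-label would change no result. They are not part of this point.

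These limits stand. They narrow the point without removing it, because nothing in the supplied text keeps the patient or the caller unaware of the arm, and the change score removes only bias that is equal on both days.

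**Conclusion.** The point holds in a limited form. A trial run exactly as the supplied protocol is written could have the pain interview conducted by someone who knows the arm, with a patient who also knows it. That leaves a subjective, tested secondary outcome unprotected against assessor and patient bias. Neither the image-based primary outcome nor the sample size is affected by this.

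The size is unknown. The false-positive rates above show only how sensitive a comparison at 113 per arm is to a small net bias. They depend on the assumed bias, complete response and a normal approximation in place of the Mann-Whitney test. They are not estimates for this trial. The case for change rests on the low cost of prevention and on the impossibility of correcting such bias afterwards.

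**What to change.** Add to the protocol:

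1. Patients are not told their allocation until after the day-14 call.
2. The day 1 and day 14 pain scores are collected with a fixed script by an existing team member who did not handle that patient's suture and cannot see the allocation field in REDCap.

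The protocol says the chart will flag participation but not whether it will show the arm. If it does, the person collecting pain should not consult that entry beforehand.

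The cost is a few sentences of protocol text, a line of consent wording, a REDCap access setting, and some loss of flexibility in scheduling calls. The protocol refers to several research personnel, so dividing the two tasks should be possible within the team, although its size is not given. The number of patients and the analysis do not change. If this is already the practice, or is stated on the pages not supplied, writing it into the protocol body is enough.

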### **Recruitment process**

Participants will be identified by their obstetrical provider and research staff as meeting inclusion criteria. The research will be introduced to the patient by their treating physician. Only upon expressed interest will the subject be approached for consent by the study team. The research personnel will be notified by the patient's treating physician of the subject's interest and the research personnel will then obtain official written consent.

Alternatively, to minimize in-person interaction during the COVID pandemic, research staff will identify the patients who are eligible for the study by reviewing the sonography schedule for patients having a nuchal translucency appointment at the correct gestational age, and then reviewing pregnancy history to identify patients who also have had a previous cesarean delivery. A HIPAA Waiver of Authorization has been attached to this submission. We will send a MyChart message/email to those patients (attached) regarding the research study, with patients being able to opt-out of the study at this time. We will then send a copy of the consent form via email (secured RedCap link). They will have the opportunity to review the consent form before we call. Next, we will contact them via phone or Mount Sinai Zoom account to review the consent form and answer any questions from them. This will be documented in EPIC. They can then sign it electronically if they agree to participate. Their participation in the study will be documented in their chart via FYI and their consent form will be scanned and uploaded into media within EPIC.

The research will be introduced to the participants by the patient's obstetrical provider. The obstetrical provider and research team will assess the patient's eligibility for the study and discuss if applicable. A consent form which details the goals and objectives of the study as well as the suture materials will be provided by the provider. Patients will be given the material to read on their own and if interested in participating, a research personnel will obtain formal

written consent and answer any questions. The provider will assess if the patient meets inclusion and exclusion criteria for participation.

Participants will undergo a medical and surgical screening prior to enrollment by their obstetrical provider. There will be no cold contacts with patients.

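### Does limiting the remote recruitment route to patients with a previous cesarean conflict with the inclusion criteria?

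*Combined protocol and SAP*

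**What the plan says.** General Design in the protocol gives three alternative ways to qualify: "those undergoing an elective scheduled cesarean delivery at" 37 weeks or later; "those in labor requiring cesarean delivery for usual obstetrical indications"; or "those who failed a trial of labor after a previous cesarean delivery". The exclusions are "multifetal gestations, placenta previas, and patients with a known coagulopathy", followed by "Also excluded are patients with IAI, patients on magnesium sulfate, placenta abruption, and PAS". A first cesarean is not among them.

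Recruitment process describes two routes. The standard one is general: "Participants will be identified by their obstetrical provider and research staff as meeting inclusion criteria". The second is a pandemic alternative: "Alternatively, to minimize in-person interaction during the COVID pandemic, research staff will identify the patients who are eligible for the study". Staff do this by looking through the schedule of nuchal translucency appointments and then "reviewing pregnancy history to identify patients who also have had a previous cesarean delivery". The study message goes to the patients found in this way.

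Consent process places the giving of study information in the third trimester and allows consent online or by phone or video call. It sets no condition on obstetric history.

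**The concern.** The remote route speaks of the eligible patients and then applies a condition that two of the three inclusion criteria do not contain. Read literally, it treats eligibility as meaning a previous cesarean. A patient having her first cesarean, scheduled or in labor, meets the criteria but can never be found this way. No section gives a reason. The timing also sits oddly: the source list is a scan visit well before delivery, while Consent process speaks of the third trimester.

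At stake would be the population to which the result applies. Background and Benefits frame the question for cesarean sections in general, and the planning mean and standard deviation come from the hospital's cesarean patients of 2018-2019, with no stated restriction by history. If much of the recruitment were remote, the trial would lean towards repeat cesareans without the protocol having said so.

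**Working it through.** **1. Eligibility against case-finding.**

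| | Previous cesarean required? |
|---|---|
| Inclusion 1, scheduled | No |
| Inclusion 2, in labor | No |
| Inclusion 3, failed trial of labor after cesarean | Yes |
| Exclusion list | First cesarean not listed |
| Provider route | No |
| Remote route | Yes |
| Consent process, including online or phone | No |

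The condition appears in one place only. A patient with a previous cesarean may qualify under any of the three criteria, so the filter selects a subset of potentially eligible patients and adds no ineligible ones. Recruitment process also has the provider assess inclusion and exclusion criteria.

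**2. Internal validity.** Product storage and preparation has the suture fetched only once randomization is done, after consent. The filter acts before allocation and applies equally to both arms. The expected share of repeat cesareans is therefore the same in each arm, and the Wilcoxon comparison of blood loss is not biased.

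**3. Case mix.** Let r be the share recruited remotely and q the share with a previous cesarean among provider-route patients. The overall share is r + (1 - r)q, so the shift caused by the filter, compared with recruiting everyone as the provider route does, is

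r + (1 - r)q - q = r(1 - q).

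The protocol gives neither r nor q. With r assumed anywhere from 5% to 50%, 226 x r runs from 226 x 0.05 = 11.3 to 226 x 0.50 = 113 patients. That counts people recruited remotely. It is only a ceiling on the shift, because some of them would have had a previous cesarean anyway. The range for r has no anchor in the document.

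**4. Sample size.** Inputs from Sample Size: control mean 534, SD 371, 30% decrease, two-sided alpha 0.05, power 0.85, inflation 15%.

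- Difference: 0.30 x 534 = 160.2; standardized, 160.2 / 371 = 0.432.
- Two-sample t-test: n = 97.28, rounded up to 98 per group.
- Inflated: 98 x 1.15 = 112.7, rounded up to 113 per group, 226 in total, as stated.
- Power at 113 / 1.15 = 98.3 per group: 0.854, matching the stated figure of about 85%.

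This confirms the arithmetic and no more. It does not show that 534 and 371 describe a mix tilted towards repeat cesareans. Because the effect is set as a percentage of the mean, the required n depends on the ratio SD / mean, here 371 / 534 = 0.695. A changed case mix would alter n only so far as it altered that ratio, and the document has no data on this by cesarean history.

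**5. What removing the filter would cost.** Scientific rationale says one third of deliveries are cesareans. If patients are consented before delivery regardless of history, consents per randomized patient = 1 / (1/3) = 3, before refusals and exclusions. Ten remote places would take about 30 consents, with about 20 patients never randomized. With the filter the figure is 1/p, where p is the chance that a consented patient with a previous cesarean goes on to a qualifying cesarean. The filter saves consents whenever p exceeds one third. The document does not give p.

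**The case for a change.** The best argument for amending is that the text claims more than the procedure delivers. It describes the step as finding eligible patients, offers no rationale for the restriction, and says nothing about recording cesarean history; Scientific rationale mentions only demographic information from the medical record. If the remote route supplied a large share of patients, recruitment channel would partly set the case mix, and a reader might not see it. A sentence explaining the filter would cost little.

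The mismatch stands, and so does the lack of a reason. The filter is nonetheless sensible on its face: at a scan visit long before delivery none of the three qualifying events has happened, and previous cesarean is a marker already in the chart that bears directly on the third criterion and plausibly on the first. That reason is inferred, not stated. Explaining the filter and showing previous cesarean in the baseline table by arm would be good documentation, and an analyst would ordinarily tabulate it from the record in any case. Neither step changes the estimate, the test or the error rates.

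Deleting the history clause alone would not settle matters, since the nuchal translucency schedule would remain the source despite the third-trimester timing in Consent process. Replacing both would widen record review and messaging, and the attached message and HIPAA waiver, which are not in the document, might need revising too. Without p, a net gain cannot be shown. The protocol's statement that there are no cold contacts, beside an opening message with an opt-out, is a separate small point of wording.

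**Conclusion.** The concern reads the text correctly but does not call for a change. The remote filter is narrower than the inclusion criteria; it is a way of finding patients within an alternative route, and the unrestricted provider route stays open beside it. No ineligible patient enters, no eligible group is shut out of the trial, and the randomized comparison is unaffected. Any effect is on the mix of first and repeat cesareans, equal to r(1 - q), and cannot be sized from the document. The 113 per group reproduces; whether the 2018-2019 mean and SD suit the eventual mix is unknown rather than shown to be safe. Recruiting without the filter would trade a broader remote pool for about three consents per randomized patient, against an unstated present yield.

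This rests on two assumptions: that the provider route operates as written throughout recruitment, and that eligibility is judged against the General Design criteria whichever way a patient was found. If recruitment turned out to be almost wholly remote, generalizability to first cesareans would need comment when results are reported, but the comparison of sutures would still be valid.
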